#### Sensitivity analyses

In addition to the sensitivity analyses described to assess the impact of missing data. The following sensitivity analyses for the primary outcome will be performed and reported to assess the robustness of the result of the main analysis in the intention-to-treat population.

- the van Elteren test with no strata
- the van Elteren test stratified by site
- the van Elteren test stratified by anticoagulation status.

#### Analyses of Secondary Outcomes

The number of days alive and not hospitalised due to heart failure has the same assumptions as the primary endpoint and will be analysed as such. Distribution of the secondary outcome continues variables will be determined by visual inspection of the histogram and by QQ plots. Normally distributed continuous variables will be compared by students' t-test and non-normal distributed continuous variables by the non-parametric Wilcoxon-Mann-Whitney-test. Categorical data will be compared using Chi-squared or exact Fisher test if  $n < 5$  in a group. Time-to-event data will be compared by the log-rank method, and adjusted analyses will be performed by proportional hazards regression. The main analysis of KCCQ scores will be a comparison of the mean score at each time point. For further exploratory analyses, the total KCCQ-score at each time point will be summarized in 25-point ranges, where scores represent health status as follows: 0 to 24: very poor to poor; 25 to 49: poor to fair; 50 to 74: fair to good; and 75 to 100: good to excellent [19].

The number and percentage of complications to thoracentesis will be reported. The number and percentage of thromboembolic events within 30 days and complications during the index admission will be compared between the groups. Results will be presented in tables, and time-to-event outcomes will be illustrated by Kaplan-Meier curves.

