### Timing of final analysis

All outcomes are analysed collectively after the 90-day follow-up of the last patient when data collection is completed.

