#### Outcome definitions and timing of outcome assessment

A detailed standard operating procedure (SOP ver. 2.0 TAP-IT data quality, collection, and definition version 28.07.22) for data collection has been prepared (key definitions summarised below)

Outcome	Type	Assessment time
Primary outcome		
Number of days alive outside hospital during the 90 days following randomisation.  Definition: A readmission is defined as admission to any department in the hospital due to any cause lasting over 24 hours or a change in calendar date.	Count, days	90 days after randomisation.
Secondary outcomes		

Number of days alive and not hospitalised due to heart failure during the 90 days following randomisation.  Definition: Readmissions meeting the above-mentioned criteria and related to heart failure based on the definition provided by The American Heart Association [11]	Count, days	90 days after randomisation.
Duration of index admission  Definition: The start date for hospitalisation in any department. The Department is registered, and the patients can be transferred between departments and hospitals (e.g. to specialised heart centres) during admission. The end of admission is defined as when the patient is discharged, either to their home facility or to care in the primary sector (nursing home, rehabilitation centre)	Count, days	From randomisation until the date of discharge from the hospital.
Changes from baseline in weight during admission  - Weight obtained within 24 hours from randomisation and discharge.	Continuous, kg	From randomisation until the date of discharge from the hospital.
Change from baseline in dosage of diuretics during admission  - Daily dose at discharge minus daily dose at baseline (both within 24 hours) - Maximum daily dose during admission minus daily dose at baseline (within 24 hours)	Furosemide-equivalent dose, Mg	From randomisation until the date of discharge from the hospital.
Time to death	Time to event, Days	90 days after randomisation.
Time to first readmission or death  Definition: A readmission is defined as admission to any department in the hospital due to any cause lasting over 24 hours or a change in calendar date.	Time to event, Day	90 days after randomisation.

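### For weight change, diuretic-dose change and, by implication, length of stay, an undefined visual check of the outcome data decides the test and with it the effect measure

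*SAP*

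**What the plan says.** The SAP section Analyses of Secondary Outcomes states that the distribution of continuous secondary variables "will be determined by visual inspection of the histogram and by QQ plots". Two branches follow: "Normally distributed continuous variables will be compared by students' t-test", and "non-normal distributed continuous variables by the non-parametric Wilcoxon-Mann-Whitney-test". It gives no criterion for calling a variable normal. It does not say whether the arms are plotted pooled or separately, or whether the person looking knows the allocation.

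The same section treats two outcomes separately. Days alive and not hospitalised for heart failure "has the same assumptions as the primary endpoint and will be analysed as such". For the questionnaire, "The main analysis of KCCQ scores will be a comparison of the mean score at each time point", with no test named.

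The outcome table leaves these numeric secondary outcomes to the general rule:

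- "Changes from baseline in weight during admission", in kg;
- "Change from baseline in dosage of diuretics during admission", in two versions (dose at discharge and maximum dose, each minus baseline);
- duration of index admission. It is typed as a count in days rather than as continuous, but the section's other rules cover only categorical and time-to-event data, so no other method is available for it.

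Three other sections bear on the point. Study design describes an open-label trial in which physicians, investigators and participants know the allocation; it does not mention analysts. Timing of final analysis says "All outcomes are analysed collectively after the 90-day follow-up of the last patient". Statistical principles sets a two-sided 0.05 level without multiplicity adjustment and promises a 95% CI for all effect estimates.

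**The concern.** The t-test and the Wilcoxon-Mann-Whitney test do not estimate the same thing. One concerns a difference in means; the other concerns the probability that a participant in one arm ranks above a participant in the other. If the choice waits for the histograms, the SAP has not said what treatment effect it will report for these outcomes, even if the judgement is made in good faith.

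The judgement is also subjective. With no threshold and no stated blinding of the person who looks, a reader of the results cannot confirm that shape alone drove the choice. Each of these p-values will be read at 0.05. The SAP shows that the problem can be avoided: under Main analysis of primary outcome it fixes the Wilcoxon-Mann-Whitney test on the expected shape, without waiting for data.

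**Working it through.** **Inputs from the SAP.** Total 126, 1:1 allocation, two-sided 0.05, and for the primary outcome a 3-day difference, SD 5 and power 90%. The SAP gives no distribution for the outcomes in question, so every shape below is an assumption.

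**Arm size.** The standardised difference is 3/5 = 0.6. The exact t-test calculation gives 60 per arm (power 90.3%), total 120. Since 120 × 1.05 = 126, the stated total is reached with about 5% added; the SAP does not say which inflation it used. Dividing 60 by 0.955, the efficiency of Wilcoxon under normality, gives 62.8, so 63 per arm and again 126. At 63 per arm the t-test has 91.6% power. The figure serves here only to set n = 126/2 = 63 per arm.

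**Does the choice change what is estimated?** Take two log-normal arms with equal means and log-scale SDs s1 and s2. The mean difference is 0 by construction. The Mann-Whitney parameter is Φ[(s1² − s2²) / (2√(s1² + s2²))].

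- s1 = 0.5, s2 = 1.0: (0.25 − 1.00)/(2 × 1.118) = −0.335, so Φ = 0.37.
- s1 = 0.6, s2 = 0.9: (0.36 − 0.81)/(2 × 1.082) = −0.208, so Φ = 0.42.

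One measure shows no effect; the other is clearly away from 0.5.

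**Type I error.** 10,000 null trials per shape, 63 per arm. The objective rule uses Shapiro-Wilk at 0.05 as a stand-in for the visual look. The column for either test counts a trial as positive if at least one of the two tests is significant.

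| Assumed shape | t-test | Wilcoxon | Objective rule | Either test | Tests disagree |
|---|---|---|---|---|---|
| Normal | 0.052 | 0.050 | 0.052 | 0.061 | 2.0% |
| Log-normal, SD 0.5 | 0.049 | 0.049 | 0.049 | 0.066 | 3.5% |
| Log-normal, SD 1 | 0.045 | 0.052 | 0.052 | 0.077 | 5.6% |
| t, 3 df | 0.049 | 0.050 | 0.052 | 0.069 | 3.9% |
| Gamma, shape 4 | 0.054 | 0.052 | 0.052 | 0.067 | 2.9% |

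Repeat simulations at the same arm size spread to 0.049–0.056 for the objective rule and 0.058–0.083 for either test.

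**Disagreement when there is an effect.** 6,000 trials each, log-normal outcomes, ratio of medians 1.3, 63 per arm. The two tests disagreed on significance in 10.5%, 18.5% and 17.5% of trials for log-scale SD 0.5, 0.75 and 1.0.

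**KCCQ.** The general rule covers continuous secondary variables and lists no exception for KCCQ. A later sentence in the same section calls for means. Read together, the specific sentence most naturally overrides the general one, but the SAP does not say so and does not name the test. The gap matters most in the sensitivity analysis under Missing data for the secondary outcome, where deaths and living non-responders score 0. A cluster at zero would look non-normal, so applying the general rule there could change the test as well as the missing-data assumption.

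**The case against.** The strongest reply is that both branches are written down in advance and the rule is conventional. Followed as written, it sends skewed data to Wilcoxon and near-normal data to the t-test, and the simulations confirm that this costs essentially nothing in type I error. The outcomes are secondary, their p-values carry no familywise protection in any case, and the primary test is fixed. All of that stands, and it limits the size of the point. It does not answer the open effect measure or the missing criterion.

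Four stronger readings are tempting, and the SAP does not support them.

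- A reader might infer that the 0.05 level fails, at 7% or more. That is the error of running both tests and keeping the better one, which the SAP does not prescribe. The shapes with the largest excess are also those that a histogram would least likely pass as normal.
- A reader might infer that unblinded analysts will choose the test. The SAP says who is unblinded and does not mention whoever inspects the plots. The supportable statement is that no safeguard is given.
- A reader might infer that every continuous secondary outcome is affected. Heart-failure days follow the primary method, and KCCQ is assigned a comparison of means.
- A reader might infer that the KCCQ sentence contradicts the general rule. It can be read as an exception to it; what is missing is the statement that it is one, and the name of the test.

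**Conclusion.** The point holds for weight change, the two diuretic-dose changes and, by inference from the lack of any other method, duration of index admission. For these, both the test and the quantity estimated depend on a visual judgement of outcome data, with no criterion and no stated blinding to arm.

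The main cost is an unspecified effect measure, which leaves the promise of a CI for every estimate without a defined target. Error-rate inflation is minor: none of note if the rule is applied objectively, and about 6 to 8% at most if the favourable test were taken. Where a skewed outcome has a real effect, roughly 10 to 19% of trials would differ in significance between the two tests, so the choice can matter for an individual result. These figures rest on 63 per arm and on assumed shapes; Shapiro-Wilk is only a proxy for a visual check.

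The primary outcome and heart-failure days are untouched. For KCCQ the defect is an unnamed test and an unstated exemption. The SAP should be corrected on these points, but the trial's main conclusion does not depend on them.

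**What to change.** Before outcome data by arm are seen, amend Analyses of Secondary Outcomes to name one test and one effect measure with its 95% CI for each outcome. For example:

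- duration of index admission and both diuretic-dose changes: Wilcoxon-Mann-Whitney, reporting the Mann-Whitney parameter with its CI, as for the primary outcome;
- weight change: mean difference with CI;
- KCCQ at each time point: mean difference with CI and a named test, stated to apply whatever the distribution, and in the sensitivity analyses as well.

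Keep histograms and QQ plots only for choosing descriptive summaries.

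The cost is a wording change, with no new data. The downside is that a test fixed in advance may be slightly less efficient for one outcome if its shape turns out differently from what was expected.

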### Randomisation

Participants are randomised with an internet-based electronic case report form and randomisation program. Randomisation is stratified according to site and whether participants are treated with oral anticoagulation therapy (regardless of type: Direct-acting oral anticoagulant or Vitamin K antagonist vs. no anticoagulation) with alternating block sizes to reduce predictability.

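### The two diuretic-dose change outcomes are compared without the baseline dose or the randomisation factors: valid, but possibly less precise than the collected data allow

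*SAP*

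**What the plan says.** The outcome table in the SAP (Outcome definitions and timing of outcome assessment) gives the diuretic outcome two forms, both simple differences in furosemide-equivalent dose: "Daily dose at discharge minus daily dose at baseline (both within 24 hours") and "Maximum daily dose during admission minus daily dose at baseline (within 24 hours"). Weight is also a change from baseline.

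Analyses of Secondary Outcomes sets the method for all continuous secondary variables: Student's t-test for those judged normal, and "non-normal distributed continuous variables by the non-parametric Wilcoxon-Mann-Whitney-test". The choice is made after inspecting histograms and QQ plots. No covariate or stratum is named. Adjustment appears in that section only for time-to-event outcomes ("Time-to-event data will be compared by the log-rank method, and adjusted analyses will be performed by proportional hazards regression"), with the covariates unlisted. The stratified van Elteren tests under Sensitivity analyses are for the primary outcome only.

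Under Randomisation: "Randomisation is stratified according to site and whether participants are treated with oral anticoagulation therapy".

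**The concern.** Dose of diuretics is a named secondary objective. A raw change score fixes the coefficient of the baseline dose at 1. Analysis of covariance estimates that coefficient from the data. When the true coefficient is well below 1, subtracting the whole baseline adds noise, and a chance difference in baseline dose between arms carries over into the estimated effect. The baseline dose must already be on file to form the change, so adjusting for it needs no new data. Leaving the stratification factors out of the analysis can also cost some precision if they predict dose.

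At stake is an interval wider than necessary on a secondary outcome. A real difference in diuretic requirement could then be missed.

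**Working it through.** **The plan's own figure.** The only sample-size figure is 126, for the primary outcome. With a difference of 3 days, SD 5, two-sided alpha 0.05 and 90% power, the normal approximation gives 2 × (1.960 + 1.282)² × 25/9 = 58.4, so 59 per arm (118). The exact t-test gives 60 per arm (120). A 5% allowance gives 120 × 1.05 = 126. The figure is reproduced, but it says nothing about diuretic dose. It is used below only for 63 per arm.

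**Inputs not in the SAP.** Rho and k are assumed throughout: rho 0.2 to 0.7, k 1 to 2.

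**Variance of ANCOVA relative to the change score.** Ratio = k²(1 − rho²) / (1 + k² − 2·rho·k). For example, rho 0.5 and k 1 give 0.75/1 = 0.75.

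**Cost of covariates.** The t-test has 126 − 2 = 124 residual degrees of freedom. Three covariates (baseline, anticoagulation, one site term) leave 121, a factor of 124/121 = 1.025. Eight leave 116, a factor of 124/116 = 1.069. Site and anticoagulation are taken as non-prognostic.

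| k | rho | Ratio | Net, 3 covariates | Net, 8 covariates |
|---|---|---|---|---|
| 1 | 0.2 | 0.600 | 0.615 | 0.641 |
| 1 | 0.5 | 0.750 | 0.769 | 0.802 |
| 1 | 0.7 | 0.850 | 0.871 | 0.909 |
| 1.5 | 0.2 | 0.815 | 0.835 | 0.871 |
| 1.5 | 0.5 | 0.964 | 0.988 | 1.031 |
| 1.5 | 0.7 | 0.998 | 1.023 | 1.067 |
| 2 | 0.2 | 0.914 | 0.937 | 0.977 |
| 2 | 0.5 | 1.000 | 1.025 | 1.069 |
| 2 | 0.7 | 0.927 | 0.950 | 0.991 |

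Interval width follows the square root. The best case is √0.615 = 0.784, about 22% narrower. The worst is √1.025 = 1.012 with three covariates, or √1.069 = 1.034 with eight.

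**Chance imbalance.** One standard error of baseline imbalance at 63 per arm is √(2/63) = 0.178 baseline SD. It shifts the change-score difference by (1 − rho·k) × 0.178 in size: 0.143 at rho 0.2, k 1; 0.089 at rho 0.5, k 1; 0 at rho 0.5, k 2.

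**Stratification factors.** If they explain a share R² of the outcome variance (assumed), the unadjusted test's true alpha is 2·(1 − Φ(1.96/√(1 − R²))): 0.048 at R² 0.02, 0.044 at 0.05 and 0.039 at 0.10. The test errs on the conservative side.

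**Skewed doses.** The ratios above belong to the t-test branch. For the Wilcoxon branch, doses were simulated as lognormal (an assumption). Rank ANCOVA had power 0.79 against 0.53 for the planned Wilcoxon test at rho 0.5, with type I error about 5%. In a separate simulation (63 per arm, log-SD 1, equal spread) the powers were:

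| rho | Planned Wilcoxon | Rank ANCOVA | Raw-scale ANCOVA |
|---|---|---|---|
| 0.5 | 0.51 | 0.75 | 0.54 |
| 0.7 | 0.73 | 0.91 | 0.71 |

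The direction favours the rank version. The size of the gain depends on the skewness and effect assumed.

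**Weight, for contrast.** At assumed rho 0.97 and k 1 the ratio is 0.0591/0.060 = 0.985, and 0.985 × 1.025 = 1.009 net. There is no gain.

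**The case against.** The strongest reply is that nothing here is wrong. An unadjusted test on a change score is a legitimate prespecified choice, its error rate is protected by randomisation, and these outcomes carry no power claim and no multiplicity control. That stands, and it limits the point to efficiency.

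It can also be said that the gain is uncertain. Maximum dose may include the baseline day and vary more than baseline, which pushes k above 1, where the gain shrinks or vanishes. The SAP does not give the number of sites, so the covariate cost could be nearer 7% than 2.5%. Raw-scale ANCOVA is little help, or slightly harmful, when doses are strongly skewed. All of this stands. It is why the result is a range and why the remedy is rank-based.

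Two stronger readings are tempting. A reader might infer that weight should be adjusted for the same reason, but the 1.009 above shows no precision gain. A reader might also infer from "Weight obtained within 24 hours from randomisation and discharge" that baseline weight is taken after drainage, which would understate weight loss in the intervention arm. The wording does not exclude this, and the dose baseline has a similar 24-hour window. But the SAP says its table summarises a data-collection SOP that is not shown and may settle the timing. A late baseline is possible under the text, not demonstrated.

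**Conclusion.** The point holds for the two diuretic-dose outcomes, as a matter of precision and chance imbalance. It does not show bias or invalidity in the planned tests, and the documents would not support that reading. Under assumed rho 0.2 to 0.7 and k 1 to 2, the net variance ratio is about 0.62 to 1.02 with three covariates and at most 1.07 with eight. The 38% reduction at the favourable end needs rho 0.2 and k 1, and should not be quoted as the expected gain. If doses are skewed, rank-based adjustment gained power in the simulations run, under assumed lognormal data. The timing of baseline weight and dose remains a query to the sponsor. Importance is low to moderate, because these are secondary outcomes.

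**What to change.** In Analyses of Secondary Outcomes, prespecify one analysis for discharge dose and for maximum dose:

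- Test by rank ANCOVA on the baseline dose, with anticoagulation status and site as further covariates. Pool small sites by a rule stated in advance.
- Report a baseline-adjusted mean difference with a bootstrap 95% interval as the effect estimate. Say that the rank test supplies the p-value, since the two can disagree near the threshold.
- For these two outcomes, drop the choice of test after inspecting the distribution.

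Leave the weight comparison as it is on precision grounds.

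Separately, confirm that the SOP takes baseline weight and dose before randomisation or drainage. If it does not, report the number of late values by arm and add a sensitivity analysis.

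The cost is SAP wording and minor analysis work, with no new data. The statistical price is about 2.5% in variance for three covariates and about 7% for eight.

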#### Secondary objectives

To determine the effectiveness of a strategy of referral to upfront thoracentesis in addition to pharmacological therapy compared with pharmacological therapy alone on admission duration, dose of

diuretics, weight loss, mortality, complications, and patient-reported outcomes such as patient satisfaction and quality of life.

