Number of complications to interventional thoracentesis:  - Pneumothorax. - Intrapleural bleeding (haemothorax) - Infection requiring antibiotics (empyema) - Pain/discomfort with the need for analgesics - Organ laceration - Re-expansion pulmonary oedema. - Thromboembolic events within 30 days from discontinued anticoagulation therapy (deep vein thrombosis, pulmonary embolism, ischemic stroke, transient ischemic attack, systemic embolism, myocardial infarction)	Count	From randomisation until the date of discharge from the hospital.
Number of complications during the index admission  - Delirium requiring pharmacological therapy - Fall - Nosocomial infections like pneumonia, urine catheter-related infection, and central venous catheter-related infections requiring a change of the catheter and antibiotic treatment.	Count	From randomisation until the date of discharge from the hospital.
Kansas City Cardiomyopathy Questionnaire score (KCCQ-23)	Scores from 0-100.  100 representing the best outcome.	14 days after discharge from index admission and 90 days after randomisation
Satisfaction with hospital stay - Selected questions from the questionnaire "Questions about your admission" from the annual Danish National Survey of Patient Experiences"	Likert scale from 1-5. 5 represents the best outcome.	14 days after discharge from index admission

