### Harms

Both treatment strategies are established practices with known side effects and complications. The study is not powered to investigate the comparative effectiveness of the intervention and comparator regarding safety and harm. The number of complications to interventional thoracentesis in the intervention group and complications during the index admission in both groups will be assessed as secondary outcomes, as specified in Table 2.

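### The comparative objective on complications has no total compared as randomised: most procedural harms are only described, and only in the intervention group

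*SAP*

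**What the plan says.** The Secondary objectives section sets a comparative question. Among the outcomes on which the two strategies are to be compared it lists "weight loss, mortality, complications, and patient-reported outcomes such as patient satisfaction and quality of life".

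The table under Outcome definitions and timing of outcome assessment holds two separate complication outcomes:

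- Complications to interventional thoracentesis: pneumothorax, haemothorax, empyema, pain needing analgesics, organ laceration, re-expansion oedema, and "Thromboembolic events within 30 days from discontinued anticoagulation therapy".
- "Number of complications during the index admission", which covers "Delirium requiring pharmacological therapy - Fall - Nosocomial infections like pneumonia" and catheter-related infections.

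The table gives both the same assessment time, from randomisation to discharge.

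Analyses of Secondary Outcomes treats the two differently. For the first, "The number and percentage of complications to thoracentesis will be reported". Then: "The number and percentage of thromboembolic events within 30 days and complications during the index admission will be compared between the groups". The Harms section repeats the split: "The number of complications to interventional thoracentesis in the intervention group and complications during the index admission in both groups" are to be assessed. It adds that the study is not powered for comparative safety and harm. Statistical principles nevertheless tests every outcome for superiority at two-sided p<0.05 without multiplicity adjustment.

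The Trial population section provides for reporting how many control participants had thoracentesis.

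**The concern.** The objective compares strategies, but the compared and uncompared events divide along a line that matters. The compared index-admission list holds general harms of a hospital stay. They are counted only until discharge, so a strategy that shortens admission also shortens the time in which they can occur. The described-only list holds most of the harms that the procedure adds. Thromboembolic events are the one item on the procedural list that is also compared.

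Two consequences follow. First, no planned result gives the share of participants in each randomised arm with any complication, so the objective is answered only in part. Second, a reader cannot rebuild that share from the publication. Two separate counts do not show how many participants had events of both kinds, and procedural events in control participants who undergo thoracentesis have no stated place.

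**Working it through.** **Step 1: what is compared.**

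| Event | Arms assessed | Compared between groups? |
|---|---|---|
| Pneumothorax, haemothorax, empyema, laceration, re-expansion oedema, pain | Intervention (Harms) | No, number and percentage only |
| Thromboembolic events within 30 days | Both (implied by the comparison) | Yes |
| Delirium, fall, nosocomial infection | Both (Harms) | Yes |
| Any complication | Not defined | No |

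**Step 2: the SAP's own figures.** It gives no complication rate. Its only relevant figure is the total of 126. A difference of 3 days with SD 5, two-sided 0.05 and 90% power needs 60 per arm by the t-test, so 120. Dividing by 0.95 gives 126.3, which agrees with 126. The sample size is not at issue. At 1:1 allocation it gives 126/2 = 63 per arm.

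**Step 3: chance of a favourable result when totals are equal.** All rates here are assumptions. Let c be the control share with an index-admission complication and p the procedural share in the intervention arm. Take no procedural events in controls, independence of the two kinds of event, and thromboembolic events left aside. Equal totals require 1 - (1 - a)(1 - p) = c, so the intervention index-admission rate is a = 1 - (1 - c)/(1 - p). For c = 30% and p = 10%, a = 1 - 0.70/0.90 = 22.2%.

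The probability of p<0.05 in favour of thoracentesis was summed exactly over the two binomial distributions. The test was chi-squared without continuity correction, or Fisher where either arm had fewer than 5 events.

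| c | p | a | Index-admission comparison | Comparison of totals |
|---|---|---|---|---|
| 15% | 5% | 10.5% | 8.4% | 2.0% |
| 15% | 10% | 5.6% | 31.5% | 2.0% |
| 20% | 5% | 15.8% | 8.3% | 2.4% |
| 20% | 10% | 11.1% | 25.4% | 2.4% |
| 30% | 5% | 26.3% | 6.7% | 2.5% |
| 30% | 10% | 22.2% | 16.7% | 2.5% |
| 30% | 20% | 12.5% | 67.7% | 2.5% |
| 40% | 5% | 36.8% | 5.9% | 2.8% |
| 40% | 10% | 33.3% | 12.3% | 2.8% |
| 40% | 20% | 25.0% | 43.9% | 2.8% |

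For p = 20%, c = 15% is impossible and c = 20% would need a = 0, so those rows are left out.

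**Step 4: one concrete table.** Take 5/63 (7.9%) in the intervention arm and 13/63 (20.6%) in controls with an index-admission complication. Chi-squared = 126 × (5×50 - 13×58)² / (63 × 63 × 18 × 108) = 4.15, p = 0.042. With a continuity correction p is about 0.075; the SAP does not say which applies. Eight further intervention participants (8/63 = 12.7%) with only a procedural event bring the totals to 13 and 13. The planned test result does not change.

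**Step 5: a smaller difference.** With assumed index-admission rates of 13.2% against 18.3%, the intervention total is 1 - 0.868 × (1 - p): 17.5%, 21.9% and 26.2% for p = 5%, 10% and 15%. The direction is lost or reversed from 10% up. A gap of this size would usually not be significant: 8 against 11 events gives p = 0.46, 8 against 12 gives p = 0.33, and the chance of a significant result favouring thoracentesis is about 11%.

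**The case against.** The plan can be defended as a coherent choice. Complications of a procedure can hardly occur in participants who do not have it, so testing them against a near-zero control count would mostly show that the procedure was done. They are a named secondary outcome, and their number and percentage will be published beside the index-admission result. The Harms section disclaims power for comparative harm. The compared outcome is labelled by its setting and its components are listed. A composite has its own problem: pain needing analgesics could dominate it, and in an open-label trial pain may be attributed to a procedure done mostly in one arm.

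Much of this stands. A reader might infer that the plan leaves all the procedure's harms out of the comparisons, conceals them, or is set to conclude that thoracentesis reduces complications. The documents support none of these. Thromboembolic events are on the procedural list and are compared, the other counts are reported, and the SAP states no rule for a conclusion on overall complications.

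Two things remain. Low power concerns differences that are missed. It does not cure a choice of events that differs in direction between the compared and the described list, and the index-admission test will yield a p-value regardless. Separate reporting also gives no participant-level total by randomised arm, least of all with procedural events confined to the intervention group. The risk of pain dominating is a reason to show the total with and without it.

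**Conclusion.** The point holds in limited form. The SAP asks a comparative question about complications and plans no as-randomised total to answer it. The index-admission comparison alone could favour thoracentesis while total complications are equal or higher.

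How likely that is cannot be settled from the SAP. Under the assumptions above (63 per arm, control index-admission rates of 15-40%, independent events, no procedural events in controls) it is a small risk at a 5% procedural rate, 6-8% against a nominal 2-3%. It becomes substantial at 10-20%. These probabilities describe cases with exactly equal totals; they do not predict this trial. The primary outcome and its sample size are unaffected. This is a cheap improvement and not a flaw that endangers the trial's main conclusion.

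**What to change.** Keep the planned comparisons and amend the SAP in four places:

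1. In Analyses of Secondary Outcomes, add a between-group comparison, by randomised arm, of the proportion of participants with at least one complication from either list in the outcome table.
2. In Harms and the outcome table, count procedural complications by the same rule and over the same window in both arms, including control participants who have thoracentesis. Fix the window for thromboembolic events here too, since their 30-day definition sits beside an assessment time that ends at discharge.
3. Show every component separately by arm, and give the total with and without pain needing analgesics.
4. State that the index-admission comparison alone does not measure overall harm.

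The cost is some wording and a few table rows. There are two downsides. The composite mixes events of very different severity, which the component display and the version without pain address. Procedural events in control participants who have thoracentesis must be recorded, and the SAP does not make clear that they are.
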